8.4.3 Pregnancy

Females of child-bearing potential are defined as all females physiologically capable of becoming pregnant. This includes female adolescent participants who are menarchal or who become menarchal during the study.

Serum/urine pregnancy tests will be performed for all female adolescents of child-bearing potential according to the Assessment Schedule (Table 8-1). A positive urine pregnancy test should be confirmed with a serum pregnancy test. Additional pregnancy tests may be performed at the investigator's discretion during the study and/or if requested by local requirements.

Participants becoming pregnant must be discontinued from study drug. However, a participant may choose to remain in the study should she become pregnant, and be followed according to the protocol-defined study visits.

All menarchal adolescents and their parent(s)/legal representative(s) should be informed about the potential risks of pregnancy and the need to prevent pregnancy during the study.

It is important to be sensitive in introducing this issue, as understanding and comprehension of puberty, sexual activity, pregnancy and contraception is influenced by age as well as, factors such as precocity, socio(educational) economic and familial background. These discussions with the participant and her parent(s)/legal representative(s) are therefore best performed by investigators familiar with the adolescent participant and her family and should be guided by requirements of the local regulatory authorities. These discussions should take into account the socio-economic, cultural factors and religious beliefs of the adolescent participant and her family. The investigator should also discuss the management of the pregnancy test results with the participant and her parent(s)/legal representative(s). The privacy of the participant should be considered in accordance with the local law and ethics.

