If an extraordinary situation (like e.g. during the coronavirus disease (COVID)-19 pandemic) limits or prevents on-site study visits, alternative methods of providing continuing care may be implemented. Phone calls, virtual contacts (e.g. teleconsult) or visits by site staff/home nursing service to the participant's home depending on local regulations and capabilities, can replace on-site study visits, for the duration of the extraordinary situation until it is safe for the participant to visit the site again. This also includes administration of study treatment by qualified study site personnel at a location other than the study site.

Novartis	
Amended Protocol Version 02 (Clean)	

Period	Screening ¹	Part 1 (Double-blind, placebo-controlled)							Part 2 (Open-label, single-arm)					
Visit Name	Screening	Day 1 (Baseline & 1st Treatment)	Day 30	Day 90	Day 150	Day 270	Day 330	Day 360 ("Switch Day") ²	Day 450	Day 510	Day 630	Day 720 (End of Treatment/ Study) ³	Safety follow-up (last visit +30 days)⁴	
Days	-28	1	30	90	150	270	330	360	450	510	630	720	750	
Informed consent / assent (as applicable)	х													
Inclusion / Exclusion criteria	х													
Demography	Х													
Pregnancy Test (serum) ⁵	х													
Pregnancy test (urine) ⁵		S						S				S		
Relevant medical history/current medical conditions	x													
Medical history Statin intolerance (if applicable)	x													
Smoking & Alcohol history	х													
Body weight / waist circumference	х	х	х	х	х	х	х	Х	х	х	х	х		
Body Height	Х	Х			Х		Х			Х		Х		
Vital Signs ⁶	Х	Х	Х	Х	Х	Х	Х	Х	Х	Х	Х	Х		
Physical Exam (complete)	S						S					S		
Physical Exam (abbreviated)		S	S	S	S	S		S	S	S	S			

Table 8-1Assessment Schedule

Novartis	
Amended Protocol Version 02 (Clean)	

Confidential

Period	Screening ¹ Part 1 (Double-blind, placebo-controlled) Part 2 (Open-label, single-arm)												
Visit Name	Screening	Day 1 (Baseline & 1st Treatment)	Day 30	Day 90	Day 150	Day 270	Day 330	Day 360 ("Switch Day") ²	Day 450	Day 510	Day 630	Day 720 (End of Treatment/ Study) ³	Safety follow-up (last visit +30 days) ⁴
Days	-28	1	30	90	150	270	330	360	450	510	630	720	750
12-lead ECG	Х						Х					Х	
Study drug administration ^{7,8}		Х		x		х		х	х		х		
IRT call	Х	Х	Х	Х	Х	Х	Х	Х	Х	Х	Х	Х	
Prior/Concomitant lipid-lowering therapy	х	х	х	x	х	х	х	х	х	х	х	х	
(Other) Prior/Concomitant Medications	x	x	х	x	x	х	х	х	x	x	х	х	
Surgical/Medical Procedures	х	х	х	x	х	х	х	х	х	х	х	х	

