LDL-apheresis recording (if applicable)	x	x	х	x	х	х	х	х	x	х	х	х	
Fasting LDL-C	Х	Х		Х	Х	Х	Х	Х	Х	Х	Х	Х	
Fasting PCSK9		Х		Х	Х		Х	Х		Х		Х	
Full fasting lipid / lipoprotein profile ⁹		Х			х		х	х		х		Х	
Anti-drug antibodies ¹⁰		Х			Х		Х			Х		Х	
Full chemistry ¹¹		Х					Х					Х	
Limited chemistry ¹¹	Х		Х	Х	Х	Х		Х	Х	Х	Х		
Hematology	Х	Х	Х		Х		Х		Х	Х		Х	
Sexual hormones		Х					Х					Х	
Urinalysis	Х	Х	Х		Х		Х		Х	Х		Х	
AEs/SAEs	Х	Х	Х	Х	Х	Х	Х	Х	Х	Х	Х	Х	
Injection site reaction assessment		Х	х	х	х	х	х	х	х	х	x	Х	

Novartis	
Amended Protocol Version 02 (Clean)	

Confidential

Period	Screening ¹		Part 1 (D	ouble-bl	ind, place	bo-contro	lled)		Part 2 (Open-labe	l, single-a	arm)	Follow-up
Visit Name	Screening	Day 1 (Baseline & 1st Treatment)	Day 30	Day 90	Day 150	Day 270	Day 330	Day 360 ("Switch Day") ²		Day 510	Day 630	Day 720 (End of Treatment/ Study) ³	Safety follow-up (last visit +30 days)⁴
Days	-28	1	30	90	150	270	330	360	450	510	630	720	750
Neurological Examination		х					х					Х	
Tanner staging / menarche		х			х		х			х		х	
Safety Follow up Call ¹⁴													S

X Assessment to be recorded in the clinical database or received electronically from a vendor

S Assessment to be recorded in the source documentation only

¹ Screening / run-in period

² Day 360 ("Switch Day") is a shared visit, i.e. the end of Part 1 and the start of Part 2 of the study

³ For participants who prematurely discontinue the study for any reason [e.g. if a participant's parent(s)/legal representative(s) / a participant (if applicable) decide to prematurely and permanently discontinue the participant from study treatment and decline further follow-up visits] an EOS visit should also be scheduled as soon as possible.

⁴ 30 days after the last study visit or 90 days after the last administration of study drug, whatever is longer

⁵ Only in females of child-bearing potential (prior to study treatment administration, if applicable)

⁶ On Day 1 and Day 360 vital signs will be measured prior to injection and 4 hours post injection; at all other visits, vital signs will be measured only once (prior to injection, if applicable).

⁷ Participants will be observed in the clinic for at least 4 hours post injection on Day 1 and Day 360 and for at least 30 minutes post injection for all other dosing visits. ⁸ For any suspected episode of anaphylaxis, the investigator will need to collect a blood sample for tryptase within 30 minutes of an onset of anaphylaxis (or as soon as possible).

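### Four of the six injection visits carry no required pregnancy test; a pre-dose urine test and a menarche question at those visits would be a cheap improvement

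*Protocol*

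**What the plan says.** Protocol Section 8.4.3 makes the schedule table govern pregnancy testing: "Serum/urine pregnancy tests will be performed for all female adolescents of child-bearing potential according to the Assessment Schedule (Table 8-1"). It defines child-bearing potential to cover girls who mature on study: "This includes female adolescent participants who are menarchal or who become menarchal during the study".

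In Table 8-1 the serum test is marked at screening only. The row "Pregnancy test (urine") is marked on Days 1, 360 and 720. The row "Study drug administration" is marked on Days 1, 90, 270, 360, 450 and 630, which agrees with the dosing days in Sections 3 and 6.1.3. Both pregnancy-test rows carry footnote 5: "Only in females of child-bearing potential (prior to study treatment administration, if applicable"). The footnote says who is tested and puts the test ahead of the dose; it adds no visits. The row "Tanner staging / menarche" is marked on Days 1, 150, 330, 510 and 720.

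On the consequence, Section 8.4.3 says: "Participants becoming pregnant must be discontinued from study drug". Section 9.1.1 lists pregnancy among the mandatory reasons to stop. Testing beyond the table is permitted but not required by the protocol itself: "Additional pregnancy tests may be performed at the investigator's discretion during the study and/or if requested by local requirements".

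**The concern.** The protocol has a mandatory stopping rule, but at four dosing visits it schedules nothing that would detect the condition before the injection. Detection there rests on symptoms, self-report, an optional test or a local requirement.

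Girls who reach menarche on study are the clearest case. A girl who is pre-menarchal at screening and on Day 1 is outside footnote 5 at both visits, so she can be dosed later without ever having had a required test. In a trial that enrols from age 12 this is foreseeable.

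What is at stake is a further dose given to a pregnant minor. Protocol Section 4.5 reports no embryofetal signal in non-clinical studies, but participants are to be told that the risk to a fetus is unknown.

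**Working it through.** The plan gives no figure to reproduce, so the check sets the rows of Table 8-1 side by side. The dosing row returns exactly the injection days stated in the text, which shows that the columns are read correctly.

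**Step 1. Tests against injections**

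| Day | Inclisiran arm | Placebo-to-inclisiran arm | Urine test | Menarche check | Days since last required urine test |
|---|---|---|---|---|---|
| 1 | active | placebo | yes | yes | same day |
| 90 | active | placebo | no | no | 90 − 1 = 89 |
| 150 | – | – | no | yes | – |
| 270 | active | placebo | no | no | 270 − 1 = 269 |
| 330 | – | – | no | yes | – |
| 360 | placebo | active | yes | no | same day |
| 450 | active | active | no | no | 450 − 360 = 90 |
| 510 | – | – | no | yes | – |
| 630 | active | active | no | no | 630 − 360 = 270 |
| 720 | – | – | yes | yes | – |

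Injections with no required same-day test: 4 of 6. Counting active doses only, it is 4 of 5 in the inclisiran arm and 2 of 3 in the placebo-to-inclisiran arm.

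**Step 2. Menarche on study**

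- First recorded on Day 150: first required test on Day 360, 360 − 150 = 210 days later, with the Day 270 injection in between.
- First recorded on Day 510: first required test on Day 720, 720 − 510 = 210 days later, with the Day 630 injection in between.
- Reached between Day 150 and Day 270: Table 8-1 does not ask until Day 330. A Day 270 test limited to girls already known to be menarchal could miss her, so the added test needs a menarche question with it.

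**Step 3. What the change does to the schedule**

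Tests would fall on Days 1, 90, 270, 360, 450, 630 and 720, at intervals of 89, 180, 90, 90, 180 and 90 days. The present intervals are 359 and 360 days. For menarche recorded on Day 150 or Day 510, the wait for a test falls to 270 − 150 = 120 or 630 − 510 = 120 days, and the test precedes the injection.

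**Step 4. Expected benefit**

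The documents do not give the number of females of child-bearing potential, a pregnancy rate or a detection window. The following are assumptions:

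- 30% to 50% of the 141 enrolled (SAP Section 1.1): 141 × 0.30 = 42.3 to 141 × 0.50 = 70.5 girls
- 0.5 to 2 pregnancies per 100 woman-years
- 14 to 42 days in which a pregnancy is detectable but unrecognised

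With 2:1 randomization, untested active doses per girl = (2/3) × 4 + (1/3) × 2 = 3.33.

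Active doses averted = girls × annual rate × 3.33 × window / 365.25:

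- Low: 42.3 × 0.005 × 3.33 × 14 / 365.25 = 0.027
- High: 70.5 × 0.02 × 3.33 × 42 / 365.25 = 0.540

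Added tests: 42.3 × 4 = 169 to 70.5 × 4 = 282. That is about 282 / 0.540 ≈ 520 tests per averted dose at the favourable end and 169.2 / 0.027 ≈ 6,300 at the other.

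**The case against.** The case for leaving the schedule alone is substantial.

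- **No standard is breached.** No visible text promises a test before each dose. A reader might infer that the protocol contradicts itself or that the schedule was an oversight. The documents do not support either. The reference list includes guidance on contraception and pregnancy testing with an access date of 28-Oct-2022, the date of Amendment 1. Most of that amendment's change table is not shown, so a rationale may exist out of view.
- **Other safeguards do most of the work.** Section 5.2 (criterion 3) requires agreement to abstinence or effective contraception, asks for review of the method at least every 3 months, and obtains advance agreement from pre-menarchal girls. Section 4.5 says that a participant whose reliable compliance is in question should not enter or continue. Section 9.1.1 stops further drug for girls who gain child-bearing potential and will not comply. Section 8.4.3 allows discretionary and locally required tests, and shows care about sensitivity, privacy and culture.
- **The count can mislead.** A reader might take four of six as four untested exposures for everyone. In the placebo arm the Day 90 and Day 270 injections contain no drug.
- **Test age is a weak argument.** A reader might rank Days 270 and 630 as worse because the last test is about nine months old. With a window of 14 to 42 days, a test 89 days old says as little about a current unrecognised pregnancy as one 269 days old, and the formula in Step 4 has no term for test age. Only the timing of the menarche checks singles out those two days.
- **The yield is small**, and a test prevents only a further dose. Section 4.2 puts the LDL-C effect of one dose at more than 6 months, so a girl who conceives between active doses already carries the drug's effect.

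All of this stands as a limit on the size of the point. It does not remove the gap: contraception review, willingness to comply and recording the date of menarche do not produce a test before a dose, and protection by local rule varies by country.

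**Conclusion.** The gap is real at protocol level: the injections on Days 90, 270, 450 and 630 need no required pregnancy test, and a girl whose menarche is recorded on Day 150 or Day 510 can receive the next injection before her first one. It is a cheap improvement to a design choice and not an error.

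The expected gain is under one averted active dose even with every assumption at its upper end. That range rests on an assumed share of girls, an assumed pregnancy rate and an assumed detection window, none of which the documents supply. The case for acting is proportionality: the event is unlikely, but the protocol forbids dosing in pregnancy and a simple test at an existing visit could prevent it. The primary analysis, alpha and power are unaffected.

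**What to change.** Amend Table 8-1 and Section 8.4.3 so that on Days 90, 270, 450 and 630:

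1. girls recorded as pre-menarchal are asked about menarche on arrival;
2. every female of child-bearing potential, including any who report menarche at that visit, has a local urine pregnancy test before the injection.

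The question must go with the test, because the scheduled menarche checks do not fall on these visits.

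The cost is a schedule amendment and up to four urine tests per affected participant at visits that already take place. Section 8.4.1 already has urine tests done locally with materials supplied by the central laboratory. The downside is more testing of adolescents, some of them abstinent. If the sponsor prefers the present schedule, a short statement of why dosing without a required test is acceptable would be the alternative.

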8.4.4 Other safety evaluations

8.4.4.1 Pubertal development

In addition to the assessment of height, weight and sexual hormones (see Section 8.4.1), the following parameters will be monitored to evaluate pubertal development, at the time points detailed in the Schedule of Assessment (Table 8-1):

- Menarche (in females)
- Tanner staging of sexual development (in males and females)

Tanner staging will performed by a physician who (re-)familiarized him/herself with the Tanner stage assessment (in case needed). The results (stages 1-5 for the respective characteristics) will be recorded on an appropriate eCRF. Once a participant reaches Tanner stage 5, evaluations can be discontinued. For females, the date of menarche will also be recorded on an appropriate eCRF.

Confidential

8.4.4.2 Neurological evaluation

A full neurological evaluation will be performed as per the Schedule of Assessment (Table 8-1). This should include assessment of motor function, sensory function, tone and reflexes and cerebellar function as detailed in Section 16.5 (Appendix 5).

Clinically significant abnormalities must be recorded on the eCRF as either Medical history/Current medical condition or AEs as appropriate.

8.4.4.3 Injection site reactions

Injection site reactions (ISRs) should be monitored at each visit from the randomization (Day 1) visit onwards (Table 8-1) and through additional contacts with the participant between visits as needed. ISRs including individual signs or symptoms at the injection site following study treatment administration should be recorded on an appropriate eCRF page. Every effort should be made to follow up with the participant until resolution of the ISR.

8.4.4.4 Anaphylactic reactions

Potential anaphylactic reactions should be assessed by Sampson criteria (see Section 16.6 (Appendix 6)). If Samson criteria are positive, confirmation by elevation of tryptase in blood plasma should be obtained within 30 minutes of the onset of anaphylaxis (or as soon as possible).

8.4.4.5 Hyperglycemia-related events

Laboratory results and newly added concomitant medications should be checked for potential hyperglycemia-related AEs.

'New onset of diabetes' should be reported as AE on the eCRF in participants with no medical history of diabetes when:

- HbA_{1c} becomes $\geq 6.5\%$ and/or
- Two consecutive values of FPG are $\geq 126 \text{ mg/dL} (7.0 \text{ mmol/L})$
- If a new concomitant medication for control of plasma glucose is added, further information to assess for a diagnosis of new onset diabetes will need to be collected

'Worsening of glycemic control' should be reported as AE on the eCRF in participants with a medical history of disease (HbA_{1c} \geq 6.5% at baseline) when:

- HbA_{1c} increases from baseline >0.5%
- New concomitant medication or increase in dose of current antidiabetic therapy is initiated to improve the control of plasma glucose level

8.4.5 Appropriateness of safety measurements

The safety assessments selected for this trial are standard for this indication/adolescent population. They take into consideration safety data from adult studies and consultations with Health Authorities and are in accordance with guidelines (ICH Harmonised Guideline Addendum to ICH E11 (ICH E11 (R1) 2017)).

8.5 Additional assessments

8.5.2 Biomarkers

No exploratory biomarkers will be evaluated in this study. The assessment of lipids/lipoproteins and PCSK9 is discussed in Section 8.3.

9 Study discontinuation and completion

9.1 Discontinuation and completion

9.1.1 Study treatment discontinuation and study discontinuation

Discontinuation of study treatment for a participant occurs when study treatment is stopped earlier than the protocol planned duration, and can be initiated by either the participant's parent(s)/legal representative(s) / participant (if applicable) or the investigator.

The investigator must discontinue study treatment for a given participant if, he/she believes that continuation would negatively impact the participant's well-being. After study treatment discontinuation, participants should remain in the study and complete other study visit procedures as per the Assessment Schedule, unless consent is withdrawn (Section 9.1.2), preferably in writing.

Study treatment must be discontinued under the following circumstances:

- Participant's parent(s)/legal representative(s) / participant (if applicable) decision
- Pregnancy
- Use of prohibited treatment as per details in the prohibited treatment section (Table 6-2)
- Following emergency unblinding
- Any situation in which study participation might result in a safety risk to the participant
- Severe and persistent (>14 days despite appropriate treatment) reactions at the injection site and any confirmed anaphylactic reactions
- Unexplained increases in transaminases (ALT or AST) or total bilirubin as follows:
 - ALT or AST >5x ULN
 - ALT or AST >3x ULN for more than 2 weeks
 - ALT or AST >3x ULN and (total bilirubin >2x ULN or INR >1.5)
 - ALT or AST >3x ULN with the appearance of fatigue, nausea, vomiting, right upper quadrant pain or tenderness, fever, rash, and/or eosinophilia (>5%)
 - The investigator should evaluate to see if other causes for the laboratory abnormalities are immediately apparent, such as obstructive gall bladder or bile duct disease, viral or alcoholic hepatitis, malignancy involving the liver, congestive hepatopathy, other hepatotoxins or heritable disorders.
- Unexplained C(P)K values >5x ULN confirmed by repeat test when the C(P)K elevation is associated with muscle pain, muscle tenderness and/or muscle weakness, or new onset renal dysfunction
- Any other laboratory abnormalities that, in the judgment of the investigator, prevents the participant from continuing study treatment

In addition, adolescent females who gain child-bearing potential during the study and are unwilling to comply with the requirements for contraception as outlined in Section 5.2 will be excluded from receiving further study drug.

If discontinuation of study treatment occurs, the investigator should make a reasonable effort to understand the primary reason for the participant's premature discontinuation of study treatment and record this information.

Study treatment may be restarted at the discretion of the investigator, if the reason for discontinuation has resolved. Every effort should be made to restart study treatment, if deemed appropriate by the investigator. Study treatment is **not** allowed to be re-started following initiation of prohibited medication that requires study drug discontinuation (Table 6-2).

Participants who discontinue study treatment or for whom the participant's parent(s)/legal representative(s) / participant (if applicable) decide that they do not to wish the participant to participate in the study further, should NOT be considered withdrawn from the study UNLESS informed consent was withdrawn (see Withdrawal of informed consent, Section 9.1.2). Where **possible, they should return for the assessments indicated** in the Assessment Schedule. If they fail to return for these assessments for unknown reasons, every effort (e.g. telephone, e-mail, letter) should be made to contact the participant's parent(s)/legal representative(s) / participant / pre-designated contact as specified in the lost to follow-up section. This contact should preferably be done according to the study visit schedule.

If the participant cannot or is unwilling to attend any visit(s), the site staff should maintain regular telephone contact with the participant, the participant's parent(s)/legal representative(s) or with another pre-designated person. This telephone contact should preferably be done according to the study visit schedule.

After study treatment discontinuation, at a minimum, in abbreviated visits, the following data should be collected at clinic visits and/or via telephone/email contact:

- New / concomitant treatments
- AEs/SAEs

Where possible, all clinic visit assessments should be performed according to Table 8-1.

The investigator must also contact the IRT to register the participant's discontinuation from study treatment.

If discontinuation occurs because the treatment code has been broken, please refer to the Emergency breaking of treatment code section (Section 6.6.3).

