6.5.1 Dose modifications

Dosing with study treatment should be temporarily interrupted as follows:

Part 1 (Year 1):

• If from the Day 150 visit onwards a participant's LDL-C is below 25 mg/dL (0.65 mmol/L) at the last visit prior to the time of the next scheduled dose, the IRT will assign blinded placebo to be administered at the next scheduled dosing visit independent of which treatment group the participant was randomized to; i.e. if the participant was treated with inclisiran, study treatment will be interrupted in a blinded fashion via the IRT.

Part 2 (Year 2):

• If from the Day 450 visit onwards a participant's LDL-C is below 25 mg/dL (0.65 mmol/L) at the last visit prior to the time of the next scheduled dose, the investigator should withhold

the dose at the next scheduled dosing visit. This will be flagged accordingly by the central laboratory.

• These dose interruptions must be recorded on an appropriate eCRF.

Treatment discontinuation is mandatory for specific events listed in Section 9.1.1.

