10.2 Additional Safety Monitoring

10.2.1 Liver safety monitoring

To ensure participant safety and enhance reliability in determining the hepatotoxic potential of an investigational drug, a standardized process for identification, monitoring and evaluation of liver events has to be followed.

Please refer to Table 16-3 (Section 16.3 (Appendix 3)) for complete definitions of liver laboratory triggers.

Once a participant is exposed to study treatment, every liver event defined in Table 16-3 should be followed up by the investigator or designated personnel at the trial site, as summarized below. Additional details on actions required in case of liver events are outlined in Table 16-4 and Table 16-5 (Section 16.3 (Appendix 3)). Requirements for follow-up of potential DILI cases is provided in Section 6.5.2.1.

- Repeat liver chemistry tests (i.e. ALT, AST, total bilirubin, direct and indirect bilirubin, PT/INR, ALP, GGT, GLDH, albumin and C(P)K) to confirm elevation.
- These liver chemistry repeats will be performed using the central laboratory. If results will not be available from the central laboratory, then the repeats can also be performed at a local laboratory to monitor the safety of the participant. If a liver event is subsequently reported,

any local liver chemistry tests previously conducted that are associated with this event should have results recorded on an appropriate eCRF.

- If the initial elevation is confirmed, close observation of the participant will be initiated, including consideration of treatment interruption if deemed appropriate.
- Discontinuation of the investigational drug (refer to the Discontinuation of study treatment section), if appropriate
- Hospitalization of the participant, if appropriate
- Causality assessment of the liver event
- Thorough follow-up of the liver event should include
 - These investigations can include based on investigator's discretion: serology tests, imaging and pathology assessments, hepatologist's consultancy; obtaining more detailed history of symptoms and prior or concurrent diseases, history of concomitant drug use, exclusion of underlying liver disease

All follow-up information and procedures performed must be recorded as appropriate in the eCRF.

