16.3 Appendix 3: Liver event and laboratory trigger definitions & follow-up requirements

Table 16-3	Liver event an	d laboratory	trigger	definitions
	Liver event an	u laboratory	uiyyei	ueminuons

Definition/ threshold		
Liver laboratory triggers	• ALT or AST > 5 × ULN	
If ALT, AST and total bilirubin normal at	• ALP > 2 × ULN (in the absence of known bone pathology)	
baseline:	• Total bilirubin > 3 × ULN (in the absence of known Gilbert syndrome)	
	 ALT or AST > 3 × ULN and INR > 1.5 	
	 Potential Hy's Law cases (defined as ALT or AST > 3 × ULN and Total bilirubin > 2 × ULN [mainly conjugated fraction] without notable increase in ALP to > 2 × ULN) 	
	Any clinical event of jaundice (or equivalent term)	
	 ALT or AST > 3 × ULN accompanied by (general) malaise, fatigue, abdominal pain, nausea, or vomiting, or rash with eosinophilia 	
	Any adverse event potentially indicative of a liver toxicity*	
If ALT or AST abnormal at baseline:	• ALT or AST > 2x baseline or > 300 U/L (whichever occurs first)	
*These events cover the following: hepatic failure, fibrosis and cirrhosis, and other liver damage-related conditions; non-infectious hepatitis; benign, malignant and unspecified liver neoplasms. ULN: upper limit of normal		

Table 16-4	Follow up requirements for liver laboratory triggers with liver
	symptoms

Confidential

	ALT or AST	Total bilirubin	Liver Symptoms	Action
ALT or	ALT or AST increase without bilirubin increase:			
	If normal at baseline: ALT or AST > 3 x ULN	Normal For participants	None	 No change to study treatment
	If elevated at baseline: ALT or AST > 2 x baseline or > 300 U/L (whichever occurs first)	with Gilbert's syndrome: No change in baseline total bilirubin		 Measure ALT, AST, ALP, GGT, total bilirubin, direct and indirect bilirubin, PT/INR, albumin, C(P)K, and GLDH in 48-72 hours Follow-up for symptoms
	If normal at baseline: ALT or AST > 5 x ULN for more than two weeks If elevated at baseline: ALT or AST > 3 x baseline or > 300 U/L (whichever occurs first) for more than two weeks	Normal For participants with Gilbert's syndrome: No change in baseline total bilirubin	None	 Interrupt study drug Measure ALT, AST, ALP, GGT, total bilirubin, direct
	If normal at baseline: ALT or AST > 8 x ULN	Normal	None	and indirect bilirubin, PT/INR, albumin, C(P)K,
ALT or	AST increase with bilirubin	increase:		and GLDH in 48-72 hours

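### For unexplained, asymptomatic ALT/AST rises with normal bilirubin, Section 9.1.1 of the protocol requires stopping in ranges where Table 16-4 leaves study treatment unchanged, and no sentence says which prevails

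*Protocol*

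**What the plan says.** Protocol Section 9.1.1 opens its list with "Study treatment must be discontinued under the following circumstances". For unexplained transaminase rises the list includes ALT or AST above 5x ULN with no duration attached, and "ALT or AST >3x ULN for more than 2 weeks". Neither limit depends on bilirubin, symptoms or baseline enzymes. Section 6.5.1 repeats the force of the list: "Treatment discontinuation is mandatory for specific events listed in Section 9.1.1".

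Table 16-4 (Section 16.3, Appendix 3) covers the same laboratory finding. Where bilirubin is normal and symptoms are given as none, its first row applies above 3x ULN for normal baseline enzymes, or above 2x baseline or 300 U/L for elevated baseline. The action is "No change to study treatment", with a repeat panel in 48 to 72 hours and follow-up for symptoms. The row has no upper bound, time limit or condition on cause. Interruption starts at "If normal at baseline: ALT or AST > 5 x ULN for more than two weeks" or at "If normal at baseline: ALT or AST > 8 x ULN". For elevated baseline it starts above 3x baseline or 300 U/L, held for more than two weeks.

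Section 10.2.1 sends the reader to Tables 16-4 and 16-5 for the actions required in liver events. It also points to the discontinuation section, but only where appropriate.

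**The concern.** The same unexplained rise can meet a compulsory stopping rule in the body of the protocol and a no-change instruction in its appendix. A site working from Table 16-4 could give the next injection to an adolescent whom Section 9.1.1 says must be stopped. An injection cannot be withdrawn once given, and Section 4.2 describes an LDL-C effect measurable for more than six months after one dose.

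Reporting is also affected. SAP Section 2.3.1 tabulates protocol deviations, including failure to withdraw a participant as the protocol requires, and SAP Section 2.4.1 summarises treatment discontinuations with reasons. Continued dosing in the conflict range is a deviation under one text and compliant under the other.

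**Working it through.** The plan states no figure to reproduce. The check sets the two rules side by side and then asks when a dosing decision would meet the conflict.

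**Step 1: normal baseline enzymes.** Take an unexplained rise with normal bilirubin and no symptoms. Let x be the multiple of ULN and w the duration in weeks.

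- Section 9.1.1: stop if x > 5, or if x > 3 and w > 2.
- Table 16-4: interrupt if x > 8, or if x > 5 and w > 2; otherwise no change if x > 3.

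| x | w | Section 9.1.1 | Table 16-4 | Result |
|---|---|---|---|---|
| 2.5 | 1 or 3 | no mandatory stop | no row applies | consistent |
| 4 | 1 | no mandatory stop | no change | consistent |
| 4 | 3 | stop | no change | conflict |
| 6 | 1 | stop | no change | conflict |
| 6 | 3 | stop | interrupt | differ in degree |
| 9 | 1 or 3 | stop | interrupt | differ in degree |

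The direct conflict covers >3x to 5x ULN beyond two weeks and >5x to 8x ULN up to two weeks.

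**Step 2: elevated baseline enzymes.** Section 9.1.1 is unchanged. Let b be the baseline multiple of ULN. Table 16-4 says no change once x/b > 2 (or the value exceeds 300 U/L), and interrupt once x/b > 3 (or the value exceeds 300 U/L) for more than two weeks. The conflict arises where a Section 9.1.1 limit and 2x baseline are both exceeded but the interruption limit is not met.

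Illustration, with assumed values: b = 2, x = 4.5, w = 3, value below 300 U/L.

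- Section 9.1.1: 4.5 > 3 and 3 weeks > 2 weeks, so stop.
- Table 16-4: 4.5/2 = 2.25, which is above 2 but not above 3, so no change.

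**Step 3: timing.** From Table 8-1, full or limited chemistry is scheduled on Days 1, 30, 90, 150, 270, 330, 360, 450, 510, 630 and 720. Injections after Day 1 are on Days 90, 270, 360, 450 and 630. The gap is the dosing day minus the latest earlier chemistry day.

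| Dosing day | Previous chemistry | Gap (days) |
|---|---|---|
| 90 | 30 | 90 − 30 = 60 |
| 270 | 150 | 270 − 150 = 120 |
| 360 | 330 | 360 − 330 = 30 |
| 450 | 360 | 450 − 360 = 90 |
| 630 | 510 | 630 − 510 = 120 |

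All five gaps exceed 14 days. A 3-5x ULN rise found at the earlier visit and persisting would be past the two-week limit at the next injection.

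All five visits count in both arms, because Section 9.1.1 concerns study treatment and so includes blinded placebo. By the dosing plan in Section 3, the injections at these visits that contain inclisiran are four in the inclisiran arm (Days 90, 270, 450, 630) and three in the placebo arm (Days 360, 450, 630).

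The >5x to 8x band up to two weeks is secondary. The shortest gap is 30 days, so it would bear on a dosing decision only through an unscheduled test.

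**The case against.** The strongest reply is that the hierarchy is clear enough. Section 9.1.1 uses compulsory language, Section 6.5.1 repeats it, and Table 16-4 is a follow-up appendix introduced as extra detail. Its first row reads naturally as a first response: keep dosing unchanged, retest within days, watch for symptoms. Section 9.1.1 also requires stopping in any situation that might put the participant at risk, the DMC reviews hepatic events (Section 10.2.3), and Section 1.1 reports no increased hepatic risk with inclisiran. Much of this stands: it supports Section 9.1.1 as the intended rule and makes harm less likely. It does not remove the conflict. The first row has no time limit, the table's own escalation by duration begins only above 5x ULN (normal baseline), and no sentence gives precedence. The word unexplained in Section 9.1.1 does not reconcile the texts either, because the first row applies whatever the cause.

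A reader might go further and infer that the 3-5x ULN band escapes the stopping rule. Section 10.2.1 says "every liver event defined in Table 16-3 should be followed up by the investigator or designated personnel at the trial site", and with normal baseline enzymes the isolated trigger in Table 16-3 is "ALT or AST > 5 × ULN". The documents do not support that inference. Section 9.1.1 applies on its own terms and needs no pointer from Section 10.2.1. The same limitation also weakens the claim that Section 10.2.1 makes Table 16-4 binding in that band. What remains is that the table lists the band and prints a contrary action beside it.

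**Conclusion.** The inconsistency is real and lies in a safety stopping rule for adolescents. It covers the two normal-baseline bands and the elevated-baseline range set out above. It could bear on any of the five dosing visits after Day 1, 30 to 120 days after the previous scheduled chemistry. Those gaps show when the conflict could apply, not how often.

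Three stronger readings are not supported:

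- **That participants were wrongly re-dosed.** The documents give no event rate, so no number affected can be stated.
- **That efficacy results are at risk.** No efficacy figure changes, and the primary estimand (SAP Section 2.5.1) uses data regardless of treatment discontinuation.
- **That the restart wording is a second contradiction.** Section 9.1.1 leaves restart to the investigator once the reason has resolved, while Table 16-4 asks for another cause and recovered enzymes. The stricter condition can be read alongside the general one, so clarifying it is optional.

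The conclusion assumes that rows and actions in Table 16-4 match in the order in which the text appears, since the table was broken in extraction. The timing argument assumes that the rise persists between visits.

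**What to change.** 1. State in Table 16-4 and in Section 10.2.1 that, for unexplained rises, the Section 9.1.1 thresholds prevail over any row of the table, for all participants regardless of baseline enzymes. The statement belongs in the table as well because Section 10.2.1 is framed around Table 16-3 events. If the sponsor wants baseline-relative limits for participants with elevated baseline enzymes, they should be written into Section 9.1.1 itself.
2. Limit the no-change row to the period pending retest, while no Section 9.1.1 threshold is met. For normal baseline enzymes and unexplained rises, that means 3-5x ULN for no more than two weeks.
3. Classify treatment discontinuations and protocol deviations against Section 9.1.1. Where dosing has already finished, this is the step that still has an effect.

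The cost is amended wording and a notice to sites. No new tests, visits or procedures are needed.
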